15.6. Search Criteria for AESI

Table 15.6.1 Search Criteria for AESI

AESI	Search Criteria
Anaphylaxis	SMQ: Anaphylaxis [Narrow]
Systemic or severe hypersensitivity reactions	SMQ: Hypersensitivity [Narrow]
Malignancy (except in situ carcinoma of the cervix, non-metastatic squamous or basal cell carcinoma of the skin)	Sub-SMQ (20000091) – Malignant or unspecified tumors
Helminthic infections	HLTs of “Helminthic infections NEC”
Suicide-related events	PTs of 
 • Completed suicide • Suicidal ideation • Depression suicidal • Suicidal behavior • Suicide attempt
Any type of conjunctivitis or blepharitis (severe or serious)	
1. Narrow conjunctivitis is defined as the following PTs
 
 • Conjunctivitis • Conjunctivitis allergic • Conjunctivitis bacterial • Conjunctivitis viral • Atopic Keratoconjunctivitis 
2. Broad conjunctivitis is defined as the following PTs
 
 • Conjunctivitis, Conjunctivitis allergic • Conjunctivitis bacterial • Conjunctivitis viral • Atopic Keratoconjunctivitis • Blepharitis • Dry eye • Eye irritation • Eye pruritus • Lacrimation increased • Eye discharge • Foreign body sensation in eyes • Photophobia, Xerophthalmia • Ocular hyperaemia • Conjunctival hyperaemia 
3. Conjunctivitis is defined as the following PTs
 
 • Conjunctivitis • Non-infective conjunctivitis

	
 • Conjunctivitis allergic • Conjunctivitis bacterial • Conjunctivitis viral • Eye irritation • Eye inflammation
Keratitis	PTs of 
 • Keratitis, Allergic keratitis • Ulcerative keratitis • Atopic keratoconjunctivitis • Herpes ophthalmic • Ophthalmic herpes simplex
Pregnancy occurring in a female patient or in a female partner of male patient administered IMP/NIMP	“Pregnancy” or “Partner Pregnancy” checked in eCRF form “Pregnancy”
Symptomatic overdose of IMP/NIMP	“Overdose of Study Treatment” or “Overdose of NIMP” checked and “Symptomatic overdose” checked in eCRF form “Overdose”

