8.3 ADVERSE EVENTS AND SERIOUS ADVERSE EVENTS

Adverse event of special interest

An adverse event of special interest (AESI) is an AE (serious or nonserious) of scientific and medical concern specific to the Sponsor's product or program, for which ongoing monitoring and immediate notification by the Investigator to the Sponsor is required. Such events may require further investigation in order to characterize and understand them. Adverse events of special interest may be added, modified or removed during a study by protocol amendment.

The following events are AESIs and require reporting to the Sponsor within 24 hours of learning of the event:

- Anaphylactic reactions
- Systemic or severe hypersensitivity reactions
- Malignancy (except in situ carcinoma of the cervix, non-metastatic squamous or basal cell carcinoma of the skin)
- Helminthic infections
- Suicide-related events
- Any type of conjunctivitis or blepharitis (severe or serious)
- Keratitis

The following events also require reporting to the Sponsor within 24 hours of learning of the event:

- Pregnancy of a female subject entered in a study as well as pregnancy occurring in a female partner of a male subject entered in a study with IMP/NIMP:
 - Pregnancy occurring in a female participant entered in the clinical trial or in a female partner of a male participant entered in the clinical trial. It will be qualified as an SAE only if it fulfills 1 of the seriousness criteria (see [Section 10.3](#) [Appendix 3]).
 - In the event of pregnancy in a female participant, IMP should be discontinued.
 - Follow-up of the pregnancy in a female participant or in a female partner of a male participant should be conducted until the outcome has been determined (See [Section 10.4](#) [Appendix 4]).
- Symptomatic overdose (serious or nonserious) with IMP/noninvestigational medicinal product (NIMP):
 - An overdose (accidental or intentional) with the IMP/NIMP is an event suspected by the Investigator or spontaneously notified by the participant and defined as at least

twice the intended dose within the intended therapeutic interval, adjusted according to the tested drug.

- Injectable administration: at least twice the dose during the planned intervals
- The circumstances (ie, accidental or intentional) should be clearly specified in the verbatim and symptoms, if any, entered on separate AE forms.

The definitions of an AE or SAE can be found in [Section 10.3](#) (Appendix 3).

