9.1.7. Adverse Events of Special Interest (AESI)

As defined in [Appendix 15.6](#), Adverse Events of Special Interest (AESI) include:

- Anaphylaxis
- Systemic or severe hypersensitivity reactions
- Malignancy (except in situ carcinoma of the cervix, non-metastatic squamous or basal cell carcinoma of the skin)
- Helminthic infections
- Suicide-related events
- Any type of conjunctivitis or blepharitis (severe or serious)
- Keratitis
- Pregnancy occurring in a female patient or in a female partner of male patient administered IMP/NIMP
- Symptomatic overdose of IMP/NIMP

The following TEAE summaries will be generated for the safety analysis set, for each treatment group and overall.

- All TEAEs of Special Interest, presented by primary SOC, HLGT, HLT and PT, showing the number and percentage of patients with at least 1 serious TEAE, sorted by internationally agreed order of primary SOC. The other levels (HLGT, HLT and PT) will be presented in alphabetical order
- All serious TEAEs of Special Interest, presented by primary SOC, HLGT, HLT and PT, showing the number and percentage of patients with at least 1 serious TEAE, sorted by internationally agreed order of primary SOC. The other levels (HLGT, HLT and PT) will be presented in alphabetical order

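### The search column of SAP Table 15.6.1 does not carry out the AESI definitions, so AESI counts are not uniquely defined and can err in either direction

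*SAP*

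**What the plan says.** Protocol 8.3 defines an AESI as an adverse event of particular concern, whether or not it is serious. Three entries in its list carry limits: "Systemic or severe hypersensitivity reactions"; "Malignancy (except in situ carcinoma of the cervix, non-metastatic squamous or basal cell carcinoma of the skin"; and conjunctivitis or blepharitis, if severe or serious. SAP 9.1.7 repeats the list after "Adverse Events of Special Interest (AESI) include" and points to Appendix 15.6 for the definition.

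Table 15.6.1 in that appendix has a label column and a search column. The label column repeats the limits, for example "Any type of conjunctivitis or blepharitis (severe or serious". The search column reads as follows:

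- Hypersensitivity: "SMQ: Hypersensitivity [Narrow", with nothing added.
- Malignancy: a sub-SMQ named "Malignant or unspecified tumors", with no exclusion step.
- Conjunctivitis or blepharitis: three lists of preferred terms (PTs). The first opens "Narrow conjunctivitis is defined as the following PTs", the second is called Broad, and the third is headed only as conjunctivitis.

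The first bullet of SAP 9.1.7 describes the table of all treatment-emergent AESIs as "showing the number and percentage of patients with at least 1 serious TEAE". The second bullet, for serious AESIs, uses the same words. SAP 9.1.5 uses them again for events leading to permanent treatment discontinuation.

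**The concern.** An AESI table is only as good as the rule that selects its events, and here the written selection rule differs from the definition. Protocol 2.3 names conjunctivitis, blepharitis, dry eye and eye pruritus among the identified reactions to dupilumab, and describes the reactions as mostly mild or moderate. Those are the events that a search without a severity condition lets in. A list without blepharitis errs the other way, because it leaves out half of what the AESI names. Taken literally, the word *serious* in the all-AESI table would also remove severe but non-serious events. Two programmers could each follow the SAP and report different AESI counts.

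**Working it through.** No sample size, power or error rate is involved, so the check compares the definitions with the search rules and the lists with each other.

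**Definition against search rule**

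| AESI | Limit in protocol 8.3 and SAP 9.1.7 | Limit in the search column |
|---|---|---|
| Hypersensitivity | systemic or severe | none |
| Malignancy | three excepted tumour types | none |
| Conjunctivitis/blepharitis | severe or serious | none |
| Overdose | symptomatic | present: a second eCRF box must be ticked |

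The overdose row shows that the search column is where qualifiers are applied. No other SAP section adds the three that are missing. What the SMQs contain cannot be seen from the documents, so whether one happens to leave out an excepted tumour is unknown.

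**The three eye lists, compared as sets**

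- Sizes: Narrow 5, Broad 16, third list 7. Four PTs are in all three, and the union has 18.
- Narrow lies wholly inside Broad. The third list does not: non-infective conjunctivitis and eye inflammation are absent from Broad, so the union is 16 + 2 = 18.
- Blepharitis is in Broad only.
- Broad divides into 5 conjunctivitis terms (counting atopic keratoconjunctivitis) + 1 blepharitis + 10 others, such as dry eye, eye pruritus and lacrimation increased. Eye irritation is in both Broad and the third list.
- The union divides into 6 conjunctivitis terms + 1 blepharitis + 11 others = 18.

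None of the lists, nor their union, equals conjunctivitis plus blepharitis.

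**Illustration.** Take six hypothetical non-serious events. They are invented to show direction and are not a forecast.

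| Event | Meets definition | Narrow | Broad | Third |
|---|---|---|---|---|
| Mild dry eye | no | no | yes | no |
| Severe blepharitis | yes | no | yes | no |
| Mild allergic conjunctivitis | no | yes | yes | yes |
| Severe bacterial conjunctivitis | yes | yes | yes | yes |
| Moderate eye irritation | no | no | yes | yes |
| Severe non-infective conjunctivitis | yes | no | no | yes |
| **Count** | **3** | **2** | **5** | **4** |

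Of the three true AESIs, Narrow finds one, Broad two and the third list two. Each list also admits at least one event that does not qualify. If the table then counted only serious events, every column would show 0.

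**The word *serious*.** Three places bear on it. Protocol 8.3 includes non-serious events. The overview in SAP 9.1 has one line for any AESI and another for serious AESIs. SAP 9.1.7 has a separate second table for serious AESIs. The first bullet conflicts with all three. In SAP 9.1.5 the phrase likewise conflicts with the overview line for any event leading to permanent discontinuation. The phrase recurs in SAP 9.1.8, where it does no harm, because death is itself a seriousness criterion (protocol 10.3).

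**The case against.** The limits are printed in the label column of the same rows and again in SAP 9.1.7. A careful programmer may read the label as the definition and the search column as the terms to look up. That stands, and it is why a reader should not conclude that every mild dry eye will be counted as an AESI. It does not settle which eye list applies. Pooling the lists does bring in blepharitis, but with eleven terms that name neither condition.

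A reader might also infer that non-serious AESIs will vanish from the report. The documents do not support that. The phrase looks like carried-over text: the bullet's own subject is all AESIs, the overview keeps the two categories apart, and an AESI listing is planned.

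Nor would severe blepharitis be lost from safety reporting. All treatment-emergent events are tabulated by PT (SAP 9.1.1) and by maximal severity (9.1.3), and serious ones again (9.1.4). The AESI tables are themselves broken down to PT, so dry eye would show on its own line. Finally, the table shells are in a separate document that is not available here and may assign the lists to outputs. These points limit the harm. They do not make the SAP's written rule match its definition.

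**Conclusion.** The point holds as a specification gap. The search rules do not carry out the AESI definitions, the eye AESI has three competing lists of which none fits, and one table description contradicts the protocol. The counts are therefore not uniquely defined and can err either way. It would go too far to say that they will be wrong, because that depends on which events occur and on how the programmer reads the label column. The size cannot be calculated, since the documents give no event rates. The effect is confined to descriptive safety tables; efficacy results and type I error are untouched. The conclusion assumes that the shells do not already resolve the choice of list. Severity: minor.

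**What to change.** 1. **Eye AESI.** Define it by one list, conjunctivitis terms plus blepharitis, and add: severity = severe OR serious = yes. Both items are recorded for each event (protocol 10.3). Label the other lists as supportive summaries.
2. **Hypersensitivity and malignancy.** Keep the SMQ searches as a first pass. Then apply the systemic-or-severe limit and the tumour exceptions by blinded medical review of the hits, with the decisions recorded. A program cannot do this alone, because the documents name no data item for *systemic* or *non-metastatic*. For double-blind events the review must precede the week 12 lock, since SAP 12 unblinds the study at that point.
3. **Wording.** In the first bullet of SAP 9.1.7, count patients with at least one TEAE of special interest. In SAP 9.1.5, count patients with at least one TEAE leading to permanent treatment discontinuation.

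The cost is an edit to one table and two sentences, minor programming and a short blinded review. SAP 1 allows such changes before database lock.

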15.7. Potentially Clinically Significant Abnormalities (PCSA) Criteria

Table 15.7.1 Potentially Clinically Significant Abnormalities Criteria

CRITERIA for POTENTIALLY CLINICALLY SIGNIFICANT ABNORMALITIES for phase 2/3 studies (oncology excepted) (From BTD-009536 May 21, 2014)		
Parameter	PCSA	Comments
HR	≤ 50 bpm and decrease from baseline ≥ 20 bpm ≥ 120 bpm and increase from baseline ≥ 20 bpm	To be applied for all positions (including missing) except STANDING.
SBP	≤ 95 mmHg and decrease from baseline ≥ 20 mmHg ≥ 160 mmHg and increase from baseline ≥ 20 mmHg	To be applied for all positions (including missing) except STANDING.
DBP	≤ 45 mmHg and decrease from baseline ≥ 10 mmHg ≥ 110 mmHg and increase from baseline ≥ 10 mmHg	To be applied for all positions (including missing) except STANDING.
Weight	$\geq 5\%$ increase from baseline $\geq 5\%$ decrease from baseline	FDA Feb 2007

15.8. Patient-Reported Outcomes (PROS)

Patient oriented eczema measure (POEM)

The POEM is a 7-item, validated questionnaire used in clinical practice and clinical trials to assess frequency of disease symptoms in children and adults (9). The format is a response to 7 items (dryness, itching, flaking, cracking, sleep loss, bleeding, and weeping) based on frequency during the past week (ie, 0 = no days, 1 = 1 to 2 days, 2 = 3 to 4 days, 3 = 5 to 6 days, and 4 = all days) with a scoring system of 0 to 28; the total score reflects disease-related severity.

POEM score will be directly provided by KONEKSA.

PROMIS Sleep Related Impairment Short Form 8a

The PROMIS is a DSM-5, Level 2, sleep disturbance measure. This study uses the 8-item PROMIS Sleep Related Impairment Short Form that assesses the domain of sleep related impairment in the past 7 days in individuals age 18 and older.

Each item asks the patient to rate the severity of the patient’s sleep related impairment during the past 7 days. Each item on the measure is rated on a 5-point scale (1 = not at all; 2 = a little bit; 3 = somewhat; 4 = quite a bit; and 5 = very much) with a range in score from 8 to 40 with higher scores indicating greater severity of sleep impairment.

Locate the applicable score conversion in [Table 15.8.1](#), and use this table to translate the total raw score or imputed total score into a PROMIS T-score for each participant. The T-score rescales the raw score into a standardized score with a mean of 50 and a standard deviation of 10. Therefore, a person with a T-score of 40 is one SD below the mean. The standardized T-score is reported as the final score for each participant.

Table 15.8.1 PROMIS Sleep-Related Impairment conversion table

Raw Score	T-score	Raw Score	T-score
8	30	25	60.3
9	35.1	26	61.3
10	38.7	27	62.3
11	41.4	28	63.3
12	43.6	29	64.3
13	45.5	30	65.3
14	47.3	31	66.3
15	48.9	32	67.3
16	50.3	33	68.4
17	51.6	34	68.5
18	52.9	35	70.7
19	54	36	71.9
20	55.1	37	73.3
21	56.1	38	75
22	57.2	39	76.9
23	58.2	40	80
24	59.3		

PROMIS score will be directly provided by KONEKSA.

Epworth Sleepiness Scale (ESS)

The ESS is a self-administered questionnaire with 8 questions. Respondents are asked to rate, on a 4-point scale (0-3), their usual chances of dozing off or falling asleep while engaged in eight different activities. Most people engage in those activities at least occasionally, although not necessarily every

day. The ESS score (the sum of 8 item scores, 0-3) can range from 0 to 24. The higher the ESS score, the higher that person's average sleep propensity in daily life, or their daytime sleepiness.

ESS score will be directly provided by KONEKSA.

Sleep Quality NRS

The Sleep Quality NRS is a simple assessment tool that patients will use to report the quality of patient's last night sleep. Patients will be asked the following question:

“On a scale of 0 to 10, with 0 being “worst possible sleep” and 10 being the “best possible sleep”, select the number that best describe the quality of your sleep last night”

Patients will complete the rating scale daily including 7 days immediately preceding the baseline visit (or daily for 5 days (from Day -7 to Day -3 prior to baseline) for patients participating in the PSG sub-study), and daily for 4 weeks (through visit 4), then daily during the week before each planned visit.

Instructions: Please complete the following question upon awakening for the day.

Select the number that best describe the quality of your sleep last night.

0	1	2	3	4	5	6	7	8	9	10	
Worst possible sleep											Best possible sleep

Patient chooses a value from 0 to 10 in the only question of the scale and that value is the global score of the scale.

Sleep Quality NRS score will be directly provided by KONEKSA.

Peak Pruritus NRS

The Peak Pruritus NRS is a simple assessment tool that patients will use to report the intensity of their pruritus (itch) during a daily recall period. Patients will be asked the following question:

“On a scale of 0 to 10, with 0 being ‘no itch’ and 10 being the ‘worst itch imaginable’ , how would you rate your itch at the worst moment during the previous 24 hours?”

Patients will complete the rating scale daily for 7 days prior to baseline (or daily for 5 days (from Day -7 to Day -3 prior to baseline) for patients participating in the PSG sub-study), and daily for 4 weeks (through visit 4), and then daily during the week before each planned visit.

On a scale of 0 to 10, with 0 being “no itch” and 10 being “worst itch imaginable”, how would you rate your itch at the worst moment during the previous 24 hours?

0	1	2	3	4	5	6	7	8	9	10
No itch										Worst itch imaginable

Patient chooses a value from 0 to 10 in the only question of the scale and that value is the global score of the scale.

Peak Pruritus NRS score will be directly provided by KONEKSA.

Skin Pain NRS

Patients will be asked to rate their skin pain using a 0 to 10 NRS. Patients will be asked the following question:

“Think about all the areas of your skin with eczema. How would you rate your skin pain at its worst in the past 24 hours?”

Patients will be asked to complete this assessment scale daily from 7 days prior to baseline through week 4 (visit 4), and then daily during the week before each planned visit.

Think about all the areas of your skin with eczema. How would you rate your skin pain at its worst in the past 24 hours?

0	1	2	3	4	5	6	7	8	9	10
No pain										Worst pain possible

Patient chooses a value from 0 to 10 in the only question of the scale and that value is the global score of the scale.

Skin Pain NRS score will be directly provided by KONEKSA.

Skin Sensitivity to touch NRS

Patients will answer the question: “Think about all the areas of your skin with eczema. How sensitive was your skin at its worst in the past 24 hours?”

This is data collected from Question 3 of the Sleep Diary: “Considering all the times you woke up last night, how much time were you awake in total?”

TST = Time of waking up for the day minus Time of falling sleep minus WASO

SOL = Time of falling sleep – Time of trying to fall sleep

$$SE = \frac{TST}{\text{Time of waking up for the day} - \text{Time of trying to fall sleep}} \times 100\%$$

Sleep diary data will be directly provided by KONEKSA.

Due to illogical data responses to the Sleep diary questionnaires, a SAP addendum with data handling rules to be applied will be provided in a separate document.

Dermatology Life Quality Index (DLQI)

The DLQI is a 10-item, validated questionnaire used in clinical practice and clinical trials to assess the impact of AD disease symptoms and treatment on Quality of Life (QoL). The format is a simple response (0 to 3 where 0 is “not at all” and 3 is “very much”) to 10 questions, which assess QoL over the past week, with an overall scoring system of 0 to 30; a high score is indicative of a poor QoL.

The DLQI score will be directly provided by KONEKSA.

Juniper Asthma Control Questionnaire (ACQ-5) [among those reporting asthmas at baseline]

The 5-question version of the Juniper asthma control questionnaire (ACQ) is a validated questionnaire to evaluate asthma control. The questionnaire will be administered only to the subset of patients with a medical history of asthma, at Baseline (Week 0), Week 12 and Week 24.

Each question is a 7-point scale (0 = no impairment to 6 = maximum impairment). A global score is calculated: the questions are equally weighted, and the ACQ-5 score is the mean of the 5 questions and, therefore, between 0 (totally controlled) and 6 (severely uncontrolled).

On the 7-point scale of the ACQ-5, a change or difference in score of 0.5 is the smallest that can be considered clinically important, corresponding to the Minimal Clinically Important Difference (MCID) defined by the developer.

ACQ-5 score will be directly provided by KONEKSA.

Allergic Rhinitis Visual Analog Scale (AR-VAS) [among those reporting allergic rhinitis at baseline]

The AR-VAS is a validated instrument for the documentation of symptoms and therapy monitoring in allergic rhinitis. Patients with comorbid AR will be provided with an ungraded VAS and will be asked to place a mark on the scale to indicate the severity of AR symptoms. Patients will be asked:

“Overall how much are your allergic symptoms bothering you today?”.

The VAS extremities will be noted as ‘Not at all bothersome’ to the left and ‘Extremely bothersome’ to the right. This questionnaire will be administered at Baseline, Week 12 and Week 24 to the patients with AR at baseline and to patients who develop AR during the study.

The AR-VAS score will be directly provided by KONEKSA.

Work Productivity and Activity Impairment Questionnaire: Atopic Dermatitis (WPAI-AD)

The WPAI-AD is designed to assess the impact of AD on the patient’s productivity. The WPAI is a 6-item, validated questionnaire to measure impairments in work and activities over a 7-day recall period. The WPAI-AD outcomes are expressed as impairment percentages, with higher numbers indicating greater impairment and less productivity.

The WPAI-AD questionnaire will be directly provided by KONEKSA.

Days missed from school or from work due to AD

Patients will complete questions about their current employment status and days missed from work/school due to their AD for all patients who are working/going to school.

Other assessments will be performed:

- Duration of employment through week 12 = sum of all employment intervals (specific assessment date – last assessment date) from the first visit till the last assessment of employment status on or prior to week 12 + 1 day. For the first post-baseline assessment, if no baseline assessment is recorded then randomization date should be used as last assessment date. Duration of employment will be calculated disregarding full or partial employment status.
- Days of sick leave through week 12 is the sum of all missed work/school days up to the last assessment date on or prior to week 12. For the first post-baseline assessment, if no baseline assessment is recorded and the number of missed days is higher than imputed employment duration then the number of missed days will be equal to employment duration.
- Employment duration adjusted sick leave days per 12 weeks will be used for treatment comparison. It is only applied for patients who are fully or partially employed. If days of sick leave through week 12 value is missing for a specific assessment, the length of this assessment interval will be deducted from the duration of employment through week 12.

Employment duration adjusted sick leave days per 12 weeks

$$= \frac{\text{Days of sick leave through week 12}}{\text{Duration (in days) of employment through week 12}} * 12 \text{ weeks (in days)}$$

Days missed from school or from work due to AD will be directly provided by KONEKSA.

Hospital Anxiety and Depression Scale (HADS)

The HADS is an instrument for assessing symptoms of anxiety and depression in non-[^]psychiatric populations; repeated administration also provides information about changes to a patient's emotional state. The HADS consists of 14 items, 7 each for anxiety and depression symptoms; possible scores range from 0 to 21 for each subscale.

The HADS scores will be directly provided by KONEKSA.

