Think about all the areas of your skin with eczema. How would you rate your skin pain at its worst in the past 24 hours?

0 1 2 3 4 5 6 7 8 9 10

No pain Worst pain possible

9. Skin Burn NRS (completed by patients)

Think about all the areas of your skin with eczema. How much did your skin burn at its worst in the past 24 hours?

[figure not shown]
0	1	2	3	4	5	6	7	8	9	10
Not										Very
at all										much

10. Skin Sensitivity to touch NRS (completed by patients)

[figure not shown]
Think about all the areas of your skin with eczema. How sensitive was your skin at its worst in the past 24 hours?

0	1	2	3	4	5	6	7	8	9	10
Normal										Extremely sensitive

[figure not shown]
11. PROMIS Sleep Related Impairment-SF8a (completed by patients)

[figure not shown]

12. Epworth Sleepiness Scale (completed by patients)

[figure not shown]

13. POEM (completed by patients)

[figure not shown]

[figure not shown]
14. DLQI (completed by patients)

[figure not shown]

15. HADS (completed by patients)

[figure not shown]

[figure not shown]
16. ACQ-5 (completed by patients)

**18. Work Productivity and Activity Impairment Questionnaire for AD (WPAI-AD)
(completed by patients)**

19. Work/School Days Missed

1. What has your employment status been since

_____ ?
(dd/mmm/yyyy)
[insert the date of last assessment]

- Employed and/or in school full time (≥ 4 days/week, cumulatively work + school)
- Employed and/or in school part time (< 4 days/week, cumulatively work + school)
- Not employed (includes retired)/Not in school

For those employed (full time or part time)/students:

2. How many days have you missed from work/school because of your skin condition since

_____ ?
(dd/mmm/yyyy)
[insert the date of last assessment]

Specify: ___ ___ ___ Days (*half days = 0.5 days*)

NOTES:

Assessment periods (i.e., time interval from the date of last assessment through the current date) must be contiguous. Leave no gaps. Cumulatively, these periods must cover the entire study duration.

Avoid duplicate reporting. If the patient missed work because of his/her skin condition on the day of assessment, this day should be recorded only once.

Record only days on which patient's skin condition prevented him/her to go to work. Otherwise, do not record the days on which the patient missed work only to participate in study visits.

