6.2.3. Health economic endpoints at baseline

- WPAI-AD: currently employed status (yes/no); number of hours missed due to AD (only if employed); number of hours missed due to other reasons (only if employed); number of hours actually worked (only if employed); NRS of atopic dermatitis affected productivity while working (only if employed) and NRS of atopic dermatitis affected ability to do regular daily activities, other than work at job
- Day missed from school or from work due to AD : patients who were employed or enrolled in school were asked to report the number of sick leave/missed school days due to AD from each assessment since the last study visit, separately for employment/school status by full time and part time

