8.2.20. Days missed from school or from work due to AD

The Days missed from school or from work will be summarized at each post-baseline visit (Week 4, Week 8, Week 12, Week 16, Week 20, and Week 24).

The total number of days of sick leave over 12 weeks will be analyzed using a negative binomial model, where days of sick leave through week 12 will be the response variable, the independent variables will be the treatment group and region, and the log transformation of duration of employment through week 12 will be used as the offset variable. No missing data will be imputed.

Sample code for negative binomial model:

```
proc genmod data = days_missed;  
class trt01pn region;
```

```
model aval = trt01pn region/ dist=negbin link=log offset=logdur;  
lsmeans trt01pn / pdiff cl exp;  
ods output lsmeandiffs=diffs lsmeans=lsmeans;  
run;
```

The duration of employment through week 12, days of sick leave through week 12 and employment duration adjusted sick leave days per 12 weeks will be summarized for each treatment group using descriptive statistics.

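### Exposure for missed work/school days is calendar time employed, and full- or part-time status enters neither the offset nor the model although it is collected

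*SAP*

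**What the plan says.** - **Exposure.** SAP 15.8 defines duration of employment through week 12 as the "sum of all employment intervals (specific assessment date – last assessment date"), plus one day. It adds: "Duration of employment will be calculated disregarding full or partial employment status".
- **Rate.** Missed days are divided by that duration and scaled to 12 weeks. SAP 15.8 says: "Employment duration adjusted sick leave days per 12 weeks will be used for treatment comparison". On who contributes: "It is only applied for patients who are fully or partially employed". Where the sick-leave count is missing for an assessment, "the length of this assessment interval will be deducted from the duration of employment through week 12".
- **Model.** SAP 8.2.20 fits a negative binomial model to total missed days through week 12, with treatment and region as the independent variables; "the log transformation of duration of employment through week 12 will be used as the offset variable".
- **What is collected.** Protocol 10.9 (Appendix 9), item 19, asks for status at each assessment. Full time is at least 4 days a week, and the other employed category is "Employed and/or in school part time (< 4 days/week, cumulatively work + school").
- **Where status is used.** SAP 6.2.3 presents missed days at baseline "separately for employment/school status by full time and part time". SAP 8.2.20 has no such split after baseline.
- **Randomisation and rank.** Stratification is by PSG participation and region only (SAP 4.2). The endpoint is exploratory (SAP Table 3.1.1) and is not in the testing order of SAP 8.2.23.

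**The concern.** An offset assumes that the expected count is proportional to the exposure entered. An absence can occur only on a day when the patient was due at work or school. With the same tendency to miss a scheduled day, someone working 2 days a week has 2/5 of the expected absences of someone working 5 days, yet both receive the same offset for the same calendar period. No other model term picks this up.

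Two things are at stake. The days per 12 weeks reported for each arm partly describe how many patients work part time. And because status is neither a stratification factor nor a covariate, a chance difference in part-time share between the arms passes into the rate ratio.

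**Working it through.** The documents give no expected rate, number employed or part-time share for this endpoint, so there is no planned figure to reproduce. Everything below beyond the SAP formula and the 4-day cut-off rests on stated assumptions.

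**1. The SAP rate at equal absence behaviour.** Assume that 10% of scheduled days are missed and the patient is employed throughout. Duration = 84 + 1 = 85 days; rate = missed days / 85 × 84.

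| Days per week | Scheduled days in 12 weeks | Missed | SAP rate per 12 weeks |
|---|---|---|---|
| 5 | 60 | 6.0 | 5.93 |
| 4 | 48 | 4.8 | 4.74 |
| 3 | 36 | 3.6 | 3.56 |
| 2 | 24 | 2.4 | 2.37 |
| 1 | 12 | 1.2 | 1.19 |

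Per scheduled day all five patients miss 10%. With 5- and 2-day schedules, an arm with 25% part time averages 0.75 × 5.93 + 0.25 × 2.37 = 5.04 days. An arm with 35% averages 0.65 × 5.93 + 0.35 × 2.37 = 4.68.

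**2. Rate ratio with no true effect.** Mean workable days per week in an arm = F(1 − p) + Pp, where F and P are the full- and part-time days per week and p is the part-time share. The apparent rate ratio is the quotient of the two arm means. Take a 10-point imbalance, 25% against 35%:

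| F and P | Mean at 25% | Mean at 35% | Ratio | Inverse |
|---|---|---|---|---|
| 4 and 3 | 3.75 | 3.65 | 1.027 | 0.973 |
| 5 and 2 | 4.25 | 3.95 | 1.076 | 0.929 |
| 5 and 1 | 4.00 | 3.60 | 1.111 | 0.900 |

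The ratio is above 1 if placebo has more part-time patients and below 1 if dupilumab has more. With equal shares it is exactly 1.

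**3. How likely a 10-point imbalance is.** SD of the difference in shares = √[p(1 − p)(1/n₁ + 1/n₂)].
- 105 employed (70 and 35), 30% part time: √[0.3 × 0.7 × (1/70 + 1/35)] = 0.095.
- 60% to 80% of 201 employed, split 2:1, 25% part time: 0.084 down to 0.072.

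Ten points is therefore 10/9.5 ≈ 1.05 to 10/7.2 ≈ 1.4 SD. Twenty points would be about 2.1 to 2.8 SD.

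**4. Illustrative simulation.** 400 runs, 94 against 47 employed patients, 5- and 2-day schedules, 10% absence per scheduled day, dispersion 1, region omitted. Cells show the mean rate ratio, with the SD of the log ratio in brackets.

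| Scenario | Planned model | With status covariate |
|---|---|---|
| True ratio 1.0, 25% part time in both arms | 1.01 (0.218) | 1.01 (0.210) |
| True ratio 0.6, 25% part time in both arms | 0.60 (0.226); power 69% | 0.60 (0.219); power 72% |
| True ratio 1.0, 35% dupilumab against 15% placebo | 0.87 (0.199) | 1.00 (0.193) |

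The Monte Carlo standard error of each power figure is about √(0.7 × 0.3/400) = 2.3 points. The same simulated data sets feed both models, but the 3-point gain should be read as small rather than exact. The last row is an imbalance larger than chance would usually produce; it shows that the covariate removes the shift.

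**The case against.** The strongest reply is that the SAP's quantity is legitimate. The endpoint is days missed to week 12, a health-economic count, and days lost per 12 calendar weeks of employment measures it directly. Absence per scheduled day is a different quantity, which neither document promises. The choice is openly stated, hours missed and hours worked are analysed separately through the WPAI-AD (SAP 8.2.19), and the split in SAP 6.2.3 would expose a baseline imbalance. Any omitted prognostic factor shifts an estimate when it happens to be unbalanced.

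Most of this stands, and it limits the point:

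- A reader might infer that the rate is not adjusted for exposure at all. The documents do not support that. Only employed or in-school intervals count, follow-up length counts, and intervals with a missing count are deducted. What is missing is an adjustment for scheduled days. Full-time patients also carry non-working days, about 2 of 7 on a 5-day week, so the difference between groups is one of degree.
- A reader might infer that the treatment comparison is biased. Randomisation balances baseline status in expectation, and with balanced shares the ratio is unbiased. The shift needs a chance imbalance, or a change in status after randomisation.
- A reader might want a scheduled-day offset. Item 19 separates only 4 or more days a week from fewer than 4, so one cannot be built from it.

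The reply does not remove the case for the covariate. The calendar-time offset would stay, so the outcome remains days lost per time employed. With a log link and a common treatment effect, adding the covariate does not change the ratio being estimated (0.60 under both models above). Seeing an imbalance at baseline does not correct for it, and adjusting after unblinding would be post hoc.

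**Conclusion.** The point holds as a modest improvement to an exploratory analysis. Full/part-time status determines how many absences are possible, is already collected, and is ignored in both the offset and the model.

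With balanced shares the cost is a few points of power. With a 10-point imbalance, which is unremarkable under the assumed employment figures, a null rate ratio moves by about 3% (4- and 3-day schedules) to 11% (5 and 1 days). On the log scale the middle case is ln 1.076 = 0.073, about one third of the simulated SD of roughly 0.22, so it would rarely decide the comparison alone. The arm-level days per 12 weeks depend on the part-time mix in every case, which matters if they are quoted as absolute work loss.

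These sizes rest on assumed schedules, part-time shares, employment rates, absence rate and dispersion. No primary or key secondary conclusion is affected.

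**What to change.** Before the week 12 database lock and unblinding, amend SAP 8.2.20 as follows:

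1. Add employment/school status at baseline (full time, part time) as a covariate in the negative binomial model, keeping the planned offset.
2. Where there is no baseline assessment, or the patient was not employed or in school at baseline, use the first recorded employed status. SAP 15.8 already foresees missing baseline assessments and SAP 8.2.20 imputes nothing, so without this rule those patients would drop out of the model.
3. Present days missed and the duration-adjusted rate by that status, as SAP 6.2.3 already does for baseline.

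The cost is one degree of freedom, one fallback rule and one table split, using data already collected. Two limits remain. Schedules still vary within each category, and later changes of status are not captured. For patients who need the fallback, the status used may have been recorded after randomisation.
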